function during flight. The primary task during the flight simulation will be to fly through the “ring target”. The cognitive test will include Mayo’s proprietary Ocular Cognitive Addition Test (OCAT, Pradhan et al. 2019) which requires subjects to look for numbers on a screen and add these numbers together. The OCAT test includes eye-tracking to measure cognitive and oculomotor performance measures (used in previous IRB approved projects – IRB # 18-005564, 18-004184, 19-004883, 16-007938). Each test will be repeated for up to GVR amplitudes (including 0mA control) presented in random order. OCAT will be conducted on a 14-inch tablet with an integrated eye-tracking sensor (EyeOn – EyeTech Digital Systems). We expect performance to decline with increasing GVR amplitude.

**Galvanic vestibular sensitivity:** We will compare motion perception at different GVR amplitudes using a similar rotator protocol as described above for the motion sickness testing. Motion perception will be quantified using the joystick. The GVR amplitudes (same range as above) will be presented in random order. Assuming a saturation effect, we will select the lowest GVR level that reduces motion perception as the amplitude for the motion sickness testing above.

A complete experimental methodology to be conducted in this protocol is shown the tables below:

Visit 1	Duration (mins)
Consent form	
Balance Performance (Dynamic Posturography): Device: Bertec Portable Essential's dual-balance plate balance system ( https://www.bertec.com/bertec-balance-advantage-systems )  Quantify dose-response for the following GVR amplitudes: Standing Eyes Open – 0mA (baseline), 1.25mA, 1.5mA, 1.75mA, and 2mA Standing Eyes Closed - 0mA (baseline), 1.25mA, 1.5mA, 1.75mA, and 2mA	10
Timed up and go (TUG):  The test will be performed for each GVR amplitudes: 0mA (baseline), 1.25mA, 1.5mA, 1.75mA and 2mA  Method: 

• The patient starts in a seated position

• The patient stands up upon on command: walks 4 meters, turns around, walks back to the chair and sits down.

	10

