
 
• An obstacle (foam block 30 cm height) will be positioned between the chair and the 4m turning point, and the patient will be required to step over this obstacle twice, once on the way toward the turning point and again on the return back.
 
• The time stops when the patient is seated.
 
	

Cognitive Performance  Device: Oculo-Cognitive Addition Test (OCAT):  0mA (baseline), 1.75mA (GVR)
	5

Galvanic Vestibular Sensitivity:  Device: Gyrostim Rotating Chair and Joystick  The chair will be rotated for up to 60 seconds with an acceleration of 10 deg/s/s to a constant velocity up to 120 deg/sec and deceleration of 10 deg/s/s to a complete stop.  5 trials of rotations will be tested for each GVR amplitudes:  0mA (baseline), 1.25mA, 1.5mA, 1.75mA and 2mA  The GVR will be turned on before each corresponding rotation.  1 minute washout period after each rotation.  Motion perception (i.e., yaw) will be measured using the joystick for each rotation.  Decide the lowest GVR amplitude that reduced motion perception, say R mA.
	20

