#### Data Analysis Plan:

We hypothesize that efficacy of galvanic vestibular reduction to reduce motion sickness severity will depend on the timing of the administration, being more effective when administered prior to stimulus (symptom) onset. For specific aim 1 we will use repeated measures ANOVA to examine changes in symptom severity, test duration (terminated at moderate nausea), and recovery to baseline across three levels: prior to stimulus (symptom) onset, following symptom onset, and placebo control. For specific aim 2 we hypothesize that functional task performance will decline with increasing levels of galvanic vestibular reduction amplitude. We will use repeated measures ANOVA to examine changes in cognitive performance, dynamic posturography, and dual tracking performance across up to 5 levels of GVR amplitude. Sample size estimates are based on: (1) the expected variability ( $s^2$ ) in the response parameters, (2) the alpha ( $\alpha$ , type I) error level, or probability of incorrectly concluding there is an effect when responses are equivalent, (3) the magnitude of the effects to be detected between the means ( $\mu_1, \mu_2$ ), and (4) the certainty (statistical power,  $1 - \beta$ ) with which the effect is to be detected. Sample sizes can be calculated based on the expected standardized differences ( $\Delta$ ) between conditions (Fisher and Van Belle 1993).

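### Aim 2 repeats each task across amplitudes in random order with no trial-position term: valid, but a balanced order plus that term would protect precision at almost no cost

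*Combined protocol and SAP*

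**What the plan says.** The Sensorimotor and cognitive test battery section states the order of testing: "Each test will be repeated for up to GVR amplitudes (including 0mA control) presented in random order". No balancing across participants is described. For the three Aim 1 sessions, by contrast, the Protocol and GVR application sections specify counterbalancing.

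Table I (first visit) gives the amplitudes per task:

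- Posturography: "0mA (baseline), 1.25mA, 1.5mA, 1.75mA, and 2mA", listed once for eyes open and once for eyes closed, 10 minutes in all.
- Timed up and go: "The test will be performed for each GVR amplitudes: 0mA (baseline), 1.25mA, 1.5mA, 1.75mA and 2mA", 10 minutes.
- OCAT: two amplitudes only, "0mA (baseline), 1.75mA (GVR"), 5 minutes.

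The only rest interval stated in Table I belongs to the chair rotations: "1 minute washout period after each rotation". None is given for posturography, timed up and go or OCAT.

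For Aim 2 the Data Analysis Plan will "use repeated measures ANOVA to examine changes in cognitive performance, dynamic posturography, and dual tracking performance across up to 5 levels of GVR amplitude". It names no term for trial position or sequence.

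**The concern.** Five timed walks over an obstacle, or five balance trials per eye condition, within about ten minutes leave room for practice or fatigue. That the trials follow closely on one another is inferred from the short task times and the absence of a stated rest. That the order is unrestricted is inferred from the absence of any balancing rule.

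If scores drift with position and the model ignores position, two things follow. The drift is counted as residual noise, which lowers power for Hypothesis 2. In the one trial actually run, some amplitudes will also fall later in the series than others by chance, so part of the drift appears in their means. At stake is how precisely the amplitude-performance relation is estimated, since this is what Aim 2 is meant to supply for adjusting amplitude during recovery.

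**Working it through.** **1. The plan's own figure.** The Power Statement gives 16 subjects for 80% power at a standardized difference of 0.75, two-sided alpha 0.05. A paired t-test with 15 df and noncentrality 0.75 × √16 = 3.0 has power 0.8006, so the figure reproduces. It does so when 0.75 is in SDs of the paired difference. With independent residuals of SD σ, a paired difference has SD √2 × σ, so the effect is 0.75 × 1.414 = 1.06 residual SDs.

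**2. Error inflation.** Assume a linear drift totalling d residual SDs from first to fifth trial. Centred positions are −2, −1, 0, 1, 2 (sum of squares 10), each step is d/4, and there are 4 within-person df. The addition to the residual variance, relative to σ², is

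10 × (d/4)² / 4 = 0.156 × d².

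This is 4% at d = 0.5, 16% at d = 1 and 63% at d = 2. Because d is squared, practice and fatigue cost the same.

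**3. Chance imbalance in the means.** Under independent random orders the position of one amplitude has variance 2, and two amplitudes have covariance −0.5. The difference in position therefore has variance 2 + 2 + 2 × 0.5 = 5, and the difference in mean position has SD √(5/n):

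- n = 30: SD 0.41, 95% limit about 0.8 positions.
- n = 40: SD 0.35, 95% limit about 0.7 positions.

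At d = 1 each position is worth 0.25 residual SD. The 2 mA versus 0 mA contrast can therefore move by up to about 0.8 × 0.25 = 0.20 residual SD at n = 30, or 0.7 × 0.25 = 0.175 at n = 40, against an effect of 1.06. The average over randomisations is zero.

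For two-trial OCAT, a first-to-second gain of g moves the contrast by g × (18 − 12)/30 = 0.2g under an 18/12 split. A split at least as uneven as 60/40 has probability 36% at n = 30 and 27% at n = 40.

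**4. Power.** Simulation of the five-level omnibus test, with a true effect of 1.06 residual SDs at 2 mA, linear in mA. Plan: random order, no position term. Fix: 10-sequence Williams order with a position factor. Figures are rounded and carry simulation error of about a point.

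| n | d | Plan | Fix |
|---|---|---|---|
| 30 | 0 | 96% | 96% |
| 30 | 0.5 | 94% | 95% |
| 30 | 1 | 93% | 97% |
| 30 | 2 | 80% | 96% |
| 40 | 1 | 99% | 99% |
| 40 | 2 | 93% | 99% |

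Sensitivity: if the true effect were only 0.75 residual SD (0.75/1.414 = 0.53 paired-difference SD, smaller than the plan's target), power at n = 30 would be 65% versus 71% at d = 1 and 48% versus 72% at d = 2.

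**5. Type I error.** Under the plan it stayed between 0.044 and 0.056 in simulations with drifts from 0 to 1.5 paired-difference SDs. Balanced order without the position term gave 0.013 at n = 30 with a drift of 1.0 paired-difference SD (1.41 residual SDs). The amplitude means are then protected, but the error term still contains the drift.

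**6. Cost in degrees of freedom.** At n = 30 the within-person df are 30 × 4 = 120. Amplitude takes 4, leaving 116 for error. A five-level position factor takes 4 more, leaving 112.

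**The case against.** The strongest reply is that the plan already has a sound safeguard. Randomising the order, with 0 mA included, makes the amplitude contrast unbiased over randomisations and keeps the test at its nominal level. That stands. A reader might infer that practice biases the amplitude means or invalidates the ANOVA; the plan's random order does not support that inference.

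A second tempting inference is that practice will hide or reverse a true decline, because Table I lists 0 mA first, labels it baseline and prints the rest in ascending order. Run that way, amplitude and position would be inseparable: a 0.75 SD decline with a 0.5 SD practice gain would show as 0.75 − 0.5 = 0.25. The documents do not support reading the table as a running order. The text says random for every test. The Galvanic vestibular sensitivity task has the same ascending list in Table I, although the text says its amplitudes are presented in random order. Table II likewise prints Prior, Midpoint and Control in a fixed sequence although those sessions are counterbalanced. What survives is that Table I could be misread by the staff who run the visit.

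Third, the loss is small for modest drift, and no document supports any particular d. That also stands, and it limits the weight of the point. Finally, a single five-level position factor would not suit every task: OCAT has two trials in Table I, and posturography has two eye conditions. The fix below allows for this.

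**Conclusion.** This is a cheap improvement in precision, not a flaw in validity. On the Power Statement's scale and with 30 participants, the plan loses about 1 point of power at d = 0.5, 4 points at d = 1 and 16 points at d = 2. Even at d = 2 it remains at about the intended 80%. At the accrual target of 40 the loss is negligible at d = 1 and about 6 points at d = 2. With no drift nothing measurable is gained or lost.

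These figures assume a linear drift, independent residuals, an effect linear in mA, complete data and five trials per task. The size of d is unknown, and unrestricted randomisation is inferred from the text's silence. The case for acting rests on the low cost and on timing: the order must be fixed before testing starts.

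**What to change.** Adopt the first two changes together, because balancing without the position term makes the test conservative.

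1. **Sensorimotor and cognitive test battery section:** replace unrestricted random order with a pre-generated balanced list. For the five-level tasks a 10-sequence Williams square puts each amplitude equally often in each position and after each other amplitude. Both 30 (3 × 10) and 40 (4 × 10) are exact multiples. Apply it within each eye condition for posturography. For two-level OCAT, let half the participants start with each condition. Treat the flight simulator task in the same way, according to its number of trials.
2. **Data Analysis Plan, Aim 2:** add trial position within each task as a within-participant factor, with as many levels as that task has trials.
3. **Table I:** state that the amplitude lists are not a running order, and reconsider the baseline label on 0 mA.

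The cost is one order list to prepare and up to 4 error degrees of freedom per task.

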effects that impact functional ability. In order to leverage our non-pharmaceutical technique that allows continuous adjustments in “dosage” level throughout recovery, we must map changes in GVR level with functional performance. Our second hypothesis is that functional task performance will decline with increasing levels of galvanic vestibular reduction. We will test this hypothesis by measuring performance on a sensorimotor and cognitive test battery in steps ranging from 0mA (control) to the level of GVR thought to provide maximal motion sickness protection. The test battery, conducted on the same subjects as specific aim 1, will include dynamic posturography as well as other cognitive and flight simulator tasks. Sensitivity to galvanic stimulation will also be obtained for each subject and used to customize the GVR amplitude for the motion sickness testing in specific aim 1. The combined deliverable from both specific aims will be to validate the efficacy of GVR when customizing the stimulus level and introducing it following symptom onset, and to understand the effects of this non-pharmaceutical approach on crew performance on functional task performance.

**Background** (*Include relevant experience, gaps in current knowledge, preliminary data, etc.):*

The rationale of our approach rests on several key principles. First, the incidence and severity of motion sickness following G-transitions poses substantial risk to the deconditioned crew during landing and subsequent recovery operations. Second, there is a well-known relationship between bilateral vestibular loss and insusceptibility to motion sickness. Third, non-pharmaceutical approaches to motion sickness mitigation typically involve vestibular habituation or desensitization training with limited retention. Fourth, galvanic vestibular reduction provides a means to mitigate motion sickness following long-duration spaceflight without dependency on retention of preflight desensitization training.

Space motion sickness represents one of the greatest clinical challenges impacting crew activities during the first few days on orbit. While the inflight incidence has varied with different spacecraft, approximately 70% experience symptoms (Lackner and Dizio 2006) and one-third experience moderate to severe symptoms (Reschke et al. 2016). Symptoms generally last 2-3 days inflight, although symptoms may persist in a small number of people (Baker et al. 2008).

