**Sensorimotor and cognitive test battery:** Our second specific aim is to evaluate the effect of GVR amplitude on functional fitness task performance. This aim is important to understand how crewmembers could titrate their GVR amplitude to retain motion sickness benefits while optimizing functional performance. For this aim, the same subjects participating in the motion sickness tests will undergo the test battery while exposed to GVR in multiple steps ranging from 0mA (control) to the level of GVR thought to provide maximal motion sickness protection. The sensorimotor test battery will include (1) dynamic posturography, (2) Timed up and go (TUG) test (3) flight simulator performance and (4) an oculo-cognitive addition test. The posture measurements will be obtained using a Bertec platform with the similar protocol used during postflight medical crew testing (Wood et al. 2015). Bertec Portable Essential's dual-balance plate balance system used for dynamic posturography is clinically used in Mayo Clinic Arizona, to test balance. For this test we will use the sensory organization test with more reliance on the vestibular system (eyes closed on unstable surface). Similarly, TUG test is clinically used in Mayo Clinic Arizona to assess an individual's functional balance. It requires appropriate static and dynamic balance system integration. TUG provides a measure of functional balance integration not provided from standing balance tasks. The flight simulator performance will use a Lockheed Martin developed Prepare3D flight simulation environment adapted to VR environment (Oculus Rift). This entire system was used in the previous IRB approved project – IRB # 18-005564. It provides simulator immersion and visuomotor

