### Endpoints

**Primary:** Our project will deliver a non-pharmaceutical countermeasure approach using galvanic vestibular reduction (GVR) that can be customized to mitigate G-transitional induced motion sickness while optimizing sensorimotor and cognitive performance.

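### OCAT, the only cognitive test in Table I, is run at 0 and 1.75 mA only, so Aim 2 learns nothing about cognition at 2 mA or between active levels

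*Combined protocol and SAP*

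**What the plan says.** The second aim (Research Question and Aims) states that "we must map changes in GVR level with functional performance", and the primary endpoint is a GVR approach "that can be customized to mitigate G-transitional induced motion sickness while optimizing sensorimotor and cognitive performance". The test battery section (Study Design and Methods) lists OCAT with posturography, the timed up and go test (TUG) and the flight simulator, all to be done "in multiple steps ranging from 0mA (control) to the level of GVR thought to provide maximal motion sickness protection". It adds: "We expect performance to decline with increasing GVR amplitude". The Data Analysis Plan uses repeated measures ANOVA to "examine changes in cognitive performance, dynamic posturography, and dual tracking performance across up to 5 levels of GVR amplitude".

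Table I is introduced as the complete methodology. It schedules posturography, TUG and the sensitivity test at 0, 1.25, 1.5, 1.75 and 2 mA. Under "Device: Oculo-Cognitive Addition Test (OCAT") it lists only "0mA (baseline), 1.75mA (GVR"), in a 5-minute slot. No reason is given for the shorter list. Table II, which covers the three later visits, contains no OCAT.

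The amplitude R for the motion sickness sessions comes from the sensitivity test: "we will select the lowest GVR level that reduces motion perception as the amplitude for the motion sickness testing above". On Table I's levels, R can be 1.25, 1.5, 1.75 or 2 mA.

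**The concern.** Aim 2 is meant to tell crew how far GVR can be turned up before performance suffers. For cognition the schedule can answer only whether 1.75 mA differs from no stimulation. It cannot compare one active level with another, and it produces no data at 2 mA, the highest amplitude in Table I.

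Only participants with R = 1.75 mA would have a cognitive result at the amplitude they receive. For R = 2 mA, cognition is measured only below that amplitude, which is the unsafe direction in which to extrapolate. For R = 1.25 or 1.5 mA, the 1.75 mA result bounds the cost from above only if decline is monotone, which the protocol expects but this schedule cannot check.

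The practical risk is that a null result at 1.75 mA is read as cognitive safety across the titration range.

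**Working it through.** **1. Degrees of freedom.** OCAT has 2 levels, so the amplitude effect has 2 − 1 = 1 degree of freedom and the ANOVA is a paired t-test of 1.75 vs 0 mA. One active level leaves 1 − 1 = 0 degrees of freedom among active levels. With five levels these become 4 and 3. Sample size does not alter this.

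**2. The plan's own power figure.** The Power Statement gives 80% power for a standardized difference of 0.75, two-sided alpha 0.05, n = 16. A paired t-test with noncentrality d√n = 0.75 × √16 = 3.0 and 15 df gives 0.801 (n = 15 gives 0.771). The figure is reproduced when 0.75 is read in SDs of the paired difference.

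**3. Assumptions for what follows.** The 0.75 applies at 2 vs 0 mA, and errors are independent with equal variance at each level. The documents give no OCAT variability and no dose-response shape, so three shapes are shown. n = 30 is the target in the Power Statement.

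**4. Effect seen by the scheduled 1.75 vs 0 mA test.**
- Linear decline from 0 mA: d = 0.75 × 1.75/2 = 0.656.
- Decline only at 2 mA: d = 0.
- Decline complete by 1.25 mA and flat after: d = 0.75.

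| Shape of decline | Scheduled 1.75 vs 0 mA, n = 16 (n = 30) | 2 vs 0 mA, n = 16 (n = 30) |
|---|---|---|
| Linear | 69% (93%) | 80% (98%) |
| Only at 2 mA | 5% (5%) | 80% (98%) |
| Complete by 1.25 mA | 80% (98%) | 80% (98%) |

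**5. Should the 2 vs 0 mA contrast wait for a significant ANOVA?** With residual SD 1, the 2 mA effect is 0.75 × √2 = 1.061. Under linear decline at n = 16 the five-level ANOVA has noncentrality 10.9 on 4 and 60 df, and power 72%. By simulation, the ANOVA and the contrast are both significant in 67%, slightly below the 69% of the scheduled test. If the SD rises by 10% or 20%, this falls to 57% or 48%. Testing both at 5% and claiming on either gives about 8.5% false positives at n = 16. A single ungated contrast keeps 5% and has 80% power.

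**6. Can five levels establish the shape?** The dose sum of squares for 1.25 to 2 mA is 0.3125. Under linear decline the slope is 1.061/2 = 0.530 per mA, so d = 0.530 × √0.3125 = 0.296. Power for a trend among active levels is 20% (35% at n = 30).

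**7. Cost of extra variance.** If more OCAT runs raise the SD of differences by 10% or 20%, d for 2 vs 0 mA becomes 0.75/1.1 = 0.682 or 0.75/1.2 = 0.625. Power at n = 16 is 72% or 65% (95% or 91% at n = 30).

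**8. Time.** Visit 1 lists 10 + 10 + 5 + 20 = 45 minutes. If the 5 minutes cover two equal OCAT runs, each takes 2.5, so three more add 7.5 minutes (17%). If the 5 minutes are per run, three more add 15 (33%). Adding only 2 mA costs 2.5 to 5 minutes.

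**The case against.** The plan breaks no rule of its own. The analysis section allows up to five levels, and two is within that. Table I speaks of quantifying a dose-response only for posturography, so OCAT may be a deliberate on/off check, kept short to limit time or practice effects. This stands: a reader might infer that the schedule contradicts the analysis plan, and the wording does not support that. What remains is a mismatch with the stated aim and with the multi-step description of the battery.

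The 5% figure depends on no effect at 1.75 mA and a full effect one 0.25 mA step later. Nothing in the documents suggests such a cliff. This also stands: it is the extreme case, and under the gradual decline the protocol expects, the gain is 69% to 80%. With 20% more variance in the longer schedule, 65% is below the scheduled 69%.

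R is the lowest amplitude that works, so R = 2 mA arises only when three lower levels fail, and the documents do not give its frequency (anywhere from 0% to 100%). Nor do they require a cognitive result at each participant's own R. Both are true. But 2 mA is an amplitude the plan can assign, and it would have no group-level cognitive result either.

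The narrative also allows up to 2.5 mA, which five levels would not cover. That stands, but Table I tests nothing above 2 mA, so R cannot exceed it on that schedule.

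**Conclusion.** The concern holds as a limit on coverage. As scheduled, Aim 2 can test whether cognition differs between 1.75 and 0 mA, and that test is sound. It cannot support a statement about titration among active levels or about 2 mA.

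The size of the gain from testing 2 mA depends on an unknown shape. At n = 16, with 0.75 SD at 2 mA and unchanged variance, it is nil if decline is complete by 1.25 mA, 11 points (69% to 80%) if linear, and 75 points (5% to 80%) if confined to 2 mA. Extra variance could cancel the gain in the linear case.

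A reader might also infer that five OCAT levels would establish a cognitive dose-response curve. They would not: 20% power for an active-level trend at n = 16 means the shape could be described but not proven. Aim 1 is unaffected. The change is worth making because it decides what Aim 2 may conclude about cognition, at small cost.

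**What to change.** Run OCAT at 0, 1.25, 1.5, 1.75 and 2 mA in random order; at minimum, add 2 mA. Pre-specify one 2 vs 0 mA contrast at two-sided 5% as the cognitive test, not conditional on the ANOVA. Report the difference from 0 mA with a 95% confidence interval at each other level as descriptive. No extra visit, participant or equipment is needed. The costs are the added Visit 1 minutes worked out above and possible practice or fatigue effects, which random order spreads over the levels but turns into variance.

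If more runs are not feasible, state in the Data Analysis Plan that cognition is a single 1.75 vs 0 mA comparison, take it out of the dose-response hypothesis, and draw no cognitive conclusion for 2 mA. This costs a sentence or two and no testing time.
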